2. Examine differences in cognitive representation, self-management behaviors, CINV severity, QOL, and resource use between, and within, the intervention and attention control groups.
3. Obtain preliminary data regarding the feasibility and acceptability of the game in older adults experiencing CINV.

This study builds on the investigators' prior work in older adults' cancer symptom experience and gaming.^{15, 16, 18-21} The eSSET-CINV intervention is expected to have a *positive impact* on the self-management choices related to CINV. Participants will use knowledge gained during game play to manage their own care resulting in observable changes in outcomes: cognitive representation, self-management behaviors, CINV severity, QOL, and resource use.

RESEARCH STRATEGY

B. SIGNIFICANCE

Adults ages 65 and older represent 13.3% (41.4 million people) of our population.²² By 2040, older adults will represent 21% of the population.²² However, older adults account for the majority of cancer diagnoses.²³ With an increasing older population, the number of older adults with cancer will also increase, taxing limited healthcare resources. These factors make managing cancer in older adults a healthcare priority.^{24, 25} Complications from cancer treatment are more common in older adults with cancer compared to younger adults.²⁶ Aging and associated limitations in organ systems that prolong plasma levels of chemotherapy (e.g., renal, gastrointestinal, and liver dysfunction^{1, 27, 28}) and increase risk of treatment-related toxicity and poor outcomes in older adults include co-morbidity, poly-pharmacy, functional and physical limitations, nutrition, emotional status, and social support (caregiver).^{1, 24} Because of this increased risk for treatment-related toxicity due to severe CINV, there is a significant need for effective educational strategies that assist older adults in making self-management decisions and taking action against CINV that are rooted in their beliefs about that symptom.

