	Standard written patient education at admission to cancer center	Standard written patient education at treatment planning visit	ENROLL/ RANDOMIZE	eSSET-CINV Intervention: 1) Game 2) Decision discussion with research nurse	Standard review of written patient education on side effects	Follow-up phone call
All subjects	x	x	IG	x	x	x
			ACG		x	x

Note: IG= Intervention Group, ACG=Attention Control Group

may act as a distraction, thus reducing anxiety. In addition, patients have already received standard written education regarding treatment effects and will expect CINV as a possible effect of treatment. Written informed consent will be obtained in a private area of the clinic open to the RN. A signed copy of the consent will be given to the patient. Once informed consent is obtained, baseline measures will be completed, and participants will be randomized (Intervention Group [IG] and Attention Control Group [ACG]) to either group by choosing an envelope with a group assignment.

Participants in each group will receive **standard care**: 1) *on admission* to the cancer center (receipt of standard written educational materials that patients are instructed to bring to each appointment), 2) *at a treatment planning visit* (receipt of specific handouts regarding treatment and potential side effects, and 3) *at time of treatment* (verbal review of chemotherapy and symptom handouts by treatment center nurses). See Table 1 for an outline of standard education and eSSET-CINV intervention.

Study Variables

Independent variable: Intervention versus Attention Control group

1) Intervention Group

The intervention will consist of two parts: 1) the eSSET-CINV game and 2) decision discussion with research nurse (RN). The game will be administered by the RN. Participants will play the game at the outpatient treatment center prior to their first chemotherapy treatment using either a study-provided laptop or smart tablet using headphones to ensure privacy and limit distraction. Please see Table 2 for the eSSET-CINV intervention process. At the end of game play, the RN will engage the participant in a discussion about the self-management choices the player made and suggest changes or discuss possible outcomes based on different choices. For example, if the player chose not to treat the avatar's mild nausea and vomiting occurred, the RN would discuss more effective self-management choices as outlined in Figure 3.

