2) Cognitive representation: The *Symptom Representation Questionnaire (SRQ)*⁹¹ has an additional 15 questions to assess cognitive representation (identity, cause, timeline, consequences, and cure/control) or beliefs about specific symptoms (0-4 agreement scale). This measure includes subscales for symptom cause (2 questions), timeline (3 questions), cure/control (3 questions), and consequence (6 questions). Only the cognitive representation of nausea will be evaluated. This tool is reliable with alpha co-efficients from 0.63 to 0.88 for the subscales.⁹¹ The cognitive representation questions will be modified at baseline to assess participants' beliefs about potential CINV consequences and their ability to be controlled/cured. Subsequent data collection time points will focus on current cognitive representations.

3) Self-management behaviors: An investigator-developed *Symptom Management Checklist [SMC]* will measure CINV: 1) self-management behaviors and 2) prevention behaviors. Participants will complete this daily at home between chemotherapy cycles. When experiencing CINV, the participant will use the SMC to record: 1) CINV severity (0-10 Likert scale) prior to self-management, 2) the *type* of self-management strategies used and, 3) the strategies *perceived helpfulness* in reducing nausea (0-10 Likert scale). Preventative self-management activities for CINV will also be recorded. All self-management strategies are coded (e.g., “MED”= taking antiemetic, “DIS”- using distraction), and the participants will fill in the strategy code they are using on the form. To lessen the risk of the SMC becoming an intervention for the Control Group, all participants will be asked to record self-management behaviors of other common treatment-related symptoms (i.e. fatigue, mouth/throat sores). The SMC will be collected by the research nurse at chemotherapy cycles 2, 3 and 4.

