Willingness to recommend the game will be assessed using one item: Would you recommend this game to other older adults about to start chemotherapy treatment (yes/no)? This will be collected at Cycle 4 (T4).

Table 3: Summary of dependent variables, measures and data collection time points

		Data Collection Time points			
Dependent Variable/Outcome s	Measure	T1 Baseline	T2 Cycle 2	T3 Cycle 3	T4 Cycle 4
Symptom severity	SRQ- patient report	x	x	x	x
Cognitive representation	SRQ-patient report	x	x	x	x
Self-management behaviors*	SMC- patient report		x	x	x
Resource Use	Patient report		x	x	x
QOL	EORTC-patient report	x	x	x	x

*Note: self-management behaviors will be recorded daily by participants, but collected by the research nurse at each treatment visit

DATA ANALYSIS

Phase I: Game prototype and production

AIM 1: Identify real-life scenarios involving CINV incidence, self-management, and consequences using a peer Community Advisory Board of older adults who have undergone cancer treatment, their family members, and oncology nurses to design and develop a serious game for CINV self-care decision making.

AIM 2: Identify design aspects and elements of eSSET-CINV game play, audio, and visual avatar development that have the greatest appeal for older adults with cancer.

Data from focus groups will be digitally audio-recorded and transcribed. Methods consistent with classic content analysis will be used to analyze data from the focus groups and will begin immediately after each focus group.⁹⁴ The focus group recordings will be reviewed by the PI and student RAs and content analysis will be conducted to thematically categorize responses. Data will be de-identified in analysis-no names will be used. In order to eliminate bias, the analysis will remain grounded in the data. Themes will be created and coded using language similar to what the participants use. These codes will then be grouped by similarity and used to summarize feedback about the game and suggestions for improvement.⁹⁴ The notes taken by the RAs during and after the focus groups will serve as a “trail of evidence” to increase the trustworthiness of the data and confirm final findings. Data are not intended to be generalized but will answer specific study AIMS.

Phase II: Game prototype testing

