Preliminary data analysis: Descriptive statistics will be provided to characterize the study participants for all demographic and experiential variables at baseline and at each treatment cycle time point. Summary tables will be provided to present participant characteristics (e.g., gender, age group, race), major study variables, game appeal, and willingness to recommend game to others. Internal consistency of study measures will be checked and evaluated to ensure data quality. Effort will be taken as much as possible to avoid missing data. If there are significant missing data that may impact analysis results, the multiple imputation method may be used for the analysis of primary endpoint. All statistical analyses will be performed using Statistical Application Packages (SAS®), version 9.4.

Principle data analysis: The primary endpoints for the study are N/V severity score and the number of self-management behaviors. The secondary endpoints are ED/hospital admission and QOL. Summary statistics for the primary and secondary endpoints will be provided. The t-test will be used if the normality of the endpoint can be confirmed. Otherwise, the Wilcoxon Rank-Sum test will be used to assess the difference between the two groups at each treatment cycle time point.

AIM 1: Estimate effect size of the eSSET-CINV in changing patient outcomes: cognitive representation, self-management behaviors, CINV severity, QOL, and resource use. The effect size of N/V severity score will be estimated using the Cohen’s d, which is defined as the difference between two means divided by a standard deviation for the data.

AIM 2: Examine differences in cognitive representation, self-management behaviors, CINV severity, QOL, and resource use, between, and within, the intervention and attention control groups. For the primary endpoints, the data will be collected over 4 treatment cycles, and the method of analysis of longitudinal data will be used to compare the difference between intervention and control groups over time. The generalized estimating equation (GEE) approach may be used to enhance the robustness of the estimation of model parameters when the ideal working correlation structure is difficult to pre-specify. In the longitudinal model treatment cycle time, interaction of time and treatment, or both, whenever feasible, may be added into the model to assess the time effect on treatment difference.

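### The cognitive representation items take a different form at T1 from T2–T4, so a within-group change from T1 cannot be read as a change in belief, and the analysis plan does not say how T1 is to be used

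*Combined protocol and SAP*

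**What the plan says.** Under Dependent Variables, item 2 (Cognitive representation), the protocol states: "The cognitive representation questions will be modified at baseline". The purpose given is to capture what participants believe about CINV they might get: its possible consequences and whether it can be controlled or cured. The next sentence reads: "Subsequent data collection time points will focus on current cognitive representations".

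Table 3 shows cognitive representation as a single SRQ measure at T1, T2, T3 and T4 and does not mark T1 as a different form.

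Phase II Aim 1 is to "Estimate effect size of the eSSET-CINV in changing patient outcomes: cognitive representation, self-management behaviors, CINV severity, QOL, and resource use". Aim 2 asks for differences in the same outcomes "between, and within, the intervention and attention control groups".

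On timing, the Recruitment and randomization section says: "Once informed consent is obtained, baseline measures will be completed, and participants will be randomized". The game follows, before the first chemotherapy treatment. T1 is therefore the only assessment made before the intervention.

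The Data Analysis section names N/V severity and the number of self-management behaviors as primary endpoints, and ED/hospital admission and QOL as secondary. Cognitive representation is in neither list. The only check planned on the instruments is internal consistency.

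**The concern.** A change score has a plain meaning only if the same thing is measured at both ends. Here the T1 items concern an anticipated symptom in patients about to have their first chemotherapy, and the later items concern beliefs held at the time. A T1-to-T2 difference within one arm has three possible sources: the different wording, the passage from expecting nausea to possibly having it, and a real change in belief. The first two would arise in both arms without any intervention.

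This matters because reframing of cognitive representation is the mechanism the protocol proposes for the game (hypothesis at the end of the Conceptual Framework section). Someone who works from Table 3 would see four scores from what looks like one scale, and could take the within-group difference asked for in Aim 2 from T1. A shift produced by the questionnaire could then be reported as reframing, in the controls as well as in the intervention group.

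**Working it through.** **Texts side by side.**

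| Question | What the documents give |
|---|---|
| Form at T1 | Modified; beliefs about potential CINV consequences and control/cure |
| Form at T2–T4 | Current representations |
| Table 3 | One SRQ measure at T1–T4, no flag |
| Measurements before the game | T1 only |
| Within-group comparison | Asked for in Aim 2; reference visit not named |
| Reliability | Alphas of 0.63 to 0.88 cited for the SRQ subscales; none for the modified form |
| Linking of the two forms | None; internal consistency only |

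Internal consistency shows whether items within one form hang together. It cannot show that two forms give the same score for the same belief. So any within-group change that starts before the game crosses an unlinked change of form.

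**Within one arm.** Let the form-related shift be s and the true change in belief be d. The expected T1-to-T2 change is d + s. One arm alone cannot separate them.

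**Between arms.** At T2, T3 or T4 both arms answer the same form, so s does not enter the comparison. For a difference in change, (d_IG + s) − (d_ACG + s) = d_IG − d_ACG when the shift is equal in both arms. As a covariate, T1 need not be on the same scale as the outcome; it only has to be measured before randomization, and it is.

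**Size, for illustration only.** The plan states no figure for this outcome, so there is nothing to reproduce. Inputs:

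- n = 33 in one arm, from Sample size and statistical power. That figure was set for nausea severity, not for this outcome.
- SD of the change score, 0.8 on the 0–4 scale: assumed.
- Shift s, 0.05 to 0.5 points: assumed.
- True change d = 0; two-sided 5% paired t-test.

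The noncentrality is s ÷ 0.8 × √33, with 32 degrees of freedom and critical value 2.037.

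| Shift s | Noncentrality | Rejection rate |
|---|---|---|
| 0 | 0 | 5% |
| 0.05 | 0.36 | 6% |
| 0.10 | 0.72 | 11% |
| 0.15 | 1.08 | 18% |
| 0.25 | 1.80 | 41% |
| 0.50 | 3.59 | 94% |

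With an assumed SD of 1.2, shifts of 0.25 and 0.5 give 21% and 64%.

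A simulation of 20,000 runs with 33 per arm and the same shift in both arms (0, 0.2, 0.3 and 0.5 SD of change) gave 5%, 20%, 39% and 79% rejection within one arm. The between-arm test of change stayed at about 5% throughout.

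**The case against.** The best reply is that the plan does not commit to the faulty contrast. Aim 2 says within groups but names no reference visit and no paired test. The longitudinal methods are introduced for the primary endpoints, and the per-visit comparisons cover the primary and secondary endpoints; cognitive representation is neither. That stands. A reader might infer that the plan requires a T1-to-T2 test and will report a wording effect as reframing. The documents do not say so: they leave the use of T1 open. What remains is that T1 is the only value before the game, so a within-group reading from T1 is the natural one and nothing rules it out.

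Second, adapting the items was reasonable. Patients having their first emetogenic chemotherapy have no treatment nausea on which to hold current beliefs. That also stands. The gap lies in the analysis, not in the choice of baseline questions.

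Third, the size is unknown. The modified items are not reproduced and may differ by little more than tense, in which case the shift could be negligible. The upper rates in the table should not be taken as expected error rates.

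A reader might also extend the point to within-group change in N/V severity, because T1 precedes chemotherapy. The documents do not describe the severity items as reworded, so no change of form arises there. A rise from a pre-chemotherapy baseline is a separate matter.

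**Conclusion.** The point holds in a limited form. The protocol uses two forms of the cognitive representation items, presents them in Table 3 as one measure, asks for within-group differences, and gives no rule for handling T1. A within-group change from T1, or an effect size built on it, would not isolate a change in belief.

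The randomised evidence is sound. Between-arm comparisons at T2–T4 are unaffected, and so are between-arm differences in change if the form-related shift is the same in both arms. A reader who concluded that the trial cannot test reframing would go too far.

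The size cannot be fixed from the documents. The range of about 6% to 94% rests wholly on the assumed SD of 0.8 and shifts of 0.05 to 0.5. The logical problem does not depend on those values, but its practical importance does. Because the outcome is the proposed mechanism yet neither a primary nor a listed secondary endpoint, this should be corrected before analysis but does not threaten the main comparison.

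**What to change.** State the following in the analysis section:

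1. Cognitive representation is analysed by comparing the arms at T2–T4, with the T1 score as a baseline covariate.
2. Within-group change in cognitive representation is limited to T2–T4, where the form is the same. Alternatively, change from T1 is reported only for items worded identically at all four visits, and is not interpreted as reframing.
3. Table 3 carries a note that the T1 form differs.

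This needs no new data, visits or patients. The price is that within-group change over T2–T4 cannot show change from before the game, because the game is played before the first treatment. Evidence of reframing then rests on the randomised comparison.

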Project Title: Promoting Cancer Symptom Management in Older Adults

Grant Number: 1R15NR015851-01

NT #: NA

Date of original submission: 12/11/2019

Date of update with cover sheet: 08/09/2021

A. SPECIFIC AIMS

This research addresses the critical need to improve symptom self-management of chemotherapy-induced nausea and vomiting (CINV) among older (≥ 65) adults by developing and testing an avatar-based Serious Game (SG) designed to build CINV self-management skills. Older adults undergoing cancer treatment are at high risk for progressive severe effects resulting from nausea and vomiting¹⁻⁴ such as fluid and electrolyte imbalances, dehydration, muscle weakness, generalized fatigue, weight loss, dizziness, altered mental status, low blood pressure, changes in cardiac function, falls, and non-adherence with treatment plans. CINV is among the top five reasons why patients call their doctor while under treatment for cancer^{5, 6} and has shown to lead to increased use of resources (e.g., unplanned emergency department (ED) and/or hospital admissions).⁷ Severe CINV-related symptoms occur in up to 80% of older adults undergoing chemotherapy treatment,² resulting in high direct and indirect costs.^{8, 9} Additionally, quality of life (QOL) and daily functioning are greatly reduced with CINV.¹⁰ Guidelines exist for treating CINV;^{11, 12} however, anti-emetics are often under-prescribed in the elderly³ and, to our knowledge, there is no evidence regarding older adults' use of anti-emetics or non-pharmacologic self-management strategies at home or within structured CINV intervention programs. Because of the increased risk for treatment-related toxicity, there is a significant need for effective educational strategies that assist older adults in making self-management decisions and taking action against CINV.

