Setting: The outpatient treatment center at the UF Health Cancer Center-Orlando will be the primary site for enrollment due to its long-standing relationship with these researchers. In 2013, UF Health Cancer Center-Orlando saw approximately 4,694 patients. Of these 2,573 patients were age 65 or older, and 565 of these patients received outpatient chemotherapy. These numbers indicate an ample sampling pool of older adults.

Sample size: The target sample is older adults receiving emetogenic chemotherapy for the first time. Sixty-six participants will be enrolled if they meet the following **inclusion criteria**: age 65 and older, newly diagnosed with any cancer, treatment with any chemotherapeutic agent with a moderate to severe emetic potential (on a 3- or 4- week cycle), proficient in English, and have a telephone. **Exclusion criteria** include: previous diagnosis and treatment for cancer, advanced or end stage disease with a palliative intent, visually or hearing impaired. Dementia or cognitive impairment is not a concern with the population since they have already been cognitively screened in order to consent to treatment at this cancer center. There will be no exclusion based on gender or racial/ethnic status. Retention of all participants will be enhanced by the following strategies 1) weekly telephone follow-up phone calls by the RA; 2) a \$50 incentive/gift card at the end of the study period; and 3) attention control group offered eSSET-CINV at the end of the study. We will oversample by 20% in order to account for attrition.

Phase II Procedures:

Recruitment and randomization: Successful recruitment and retention strategies previously established by the team will be used during this phase.^{7, 15, 16, 18, 90} Convenience sampling, followed by randomization will be used. All new patients will be screened for eligibility by the Research Nurse (RN-PG) using the Sunrise XA -

electronic medical record system used by Orlando Health. Eligible patients will be approached by the RN at their first chemotherapy appointment and asked to participate. This timing is not expected to add to or create patient anxiety. Patients usually wait 30 to 60 minutes for lab results and chemotherapy to be delivered. Participating

Table 1: Intervention schema

	Pre-treatment		First Treatment Visit			Post - treatment

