Participant characteristics: Demographic and experiential characteristics that may influence CINV and ability to self-manage this symptom will be measured at T1 (baseline). Demographics include: age, gender, comorbidity information, education level, and income level. Experiential characteristics include: cancer diagnosis and stage, chemotherapy regimen with antiemetics, discharge antiemetic prescriptions, use of the Internet to research symptom management information, and caregiver presence (yes/no) and involvement at home. All cancer information will be collected from the patient's electronic medical record by the RN. Delays in chemotherapy treatment and rationale for delay will also be recorded at each time point by the RN.

Dependent Variables

An overview of study variables, measures and data collection timeline are presented in Table 3. Data will be collected for 4 treatment cycles (3 or 4 months depending on cycle length). Questionnaires will use a paper/pencil format with enlarged font and be entered into Excel™ software.

1) Symptom severity: The *Symptom Representation Questionnaire (SRQ)*⁹¹, a 24-item self-report measure will be used to identify presence and severity of common treatment-related symptoms (0-10 Likert scale), including nausea and vomiting (N/V). This measure asks respondents to think about their symptoms over the past week.

Table 2: eSSET-CINV Intervention process

1	Game introduction and orientation
2	Choose avatar
3	Avatar discharged home after treatment
4	Avatar begins to experience nausea
5	Player makes self-management decisions
6	Avatar responds based on player decisions
7	Avatar experience continues with periodic nausea as player continues to make self-management decisions
8	Game ends when avatar achieves goal of mild or no nausea or has an unplanned ED or hospital admission
9	Discussion of decision choices with Research Nurse

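### Both primary endpoints and QOL are collected only at chemotherapy visits for Cycles 2 to 4, with no stated route for participants who stop or skip a cycle, so the loss can be informative

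*Combined protocol and SAP*

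**What the plan says.** Under Principle data analysis: "The primary endpoints for the study are N/V severity score and the number of self-management behaviors". Table 3 places the SRQ and the EORTC at baseline (T1) and at Cycles 2, 3 and 4 (T2 to T4), on paper forms. The SMC diary is kept at home, and its handover depends on a visit. The Dependent Variables section says "The SMC will be collected by the research nurse at chemotherapy cycles 2, 3 and 4", and the note to Table 3 says "self-management behaviors will be recorded daily by participants, but collected by the research nurse at each treatment visit".

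The weekly calls ask how participants are and remind them to keep the diary. The outcomes that the text assigns to calls are unplanned ED/hospital admission (calls and visits) and the game appeal survey (first call).

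The Specific Aims end their list of severe effects of nausea and vomiting with "falls, and non-adherence with treatment plans".

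Four provisions bear on participants who go off schedule:
- Participant characteristics: "Delays in chemotherapy treatment and rationale for delay will also be recorded at each time point by the RN".
- Sample size: "We will oversample by 20% in order to account for attrition".
- Preliminary data analysis: multiple imputation is optional for the primary endpoint, with no model given.
- AIM 2 analysis: the window that defines a treatment cycle is still to be determined.

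**The concern.** A participant who stops for good after receiving a cycle has no next chemotherapy visit. The diary covering that cycle, which includes 0-10 severity ratings, may be complete at home with no stated way to reach the study. The SRQ and EORTC due at the next visit are not taken. For someone who stops after Cycle 1, that leaves no post-baseline data on either primary endpoint or on QOL. A skipped cycle has no rule at all.

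By the protocol's own rationale, nausea and vomiting can cause departure from treatment. Missingness may then depend on the very scores that are missing, and differ between arms if the game works. Aim 1 of Phase II is to estimate an effect size. An estimate from those still attending could describe a selected group, and it is the main figure a later trial would use.

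**Working it through.** **Routes for data after stopping or skipping a cycle**

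| Outcome | Role | Stated route without a chemotherapy visit |
|---|---|---|
| N/V severity (SRQ) | primary | none |
| Self-management behaviors (SMC) | primary | recorded at home; no return route |
| QOL (EORTC) | secondary | none |
| ED/hospital admission | secondary | phone; checked against records where possible |
| Game appeal | additional | phone, first call |

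**Whether the safeguards fill the gap.** Oversampling restores numbers, not the missing scores. The per-cycle t-test or Wilcoxon test uses attenders only. Standard repeated measures ANOVA drops incomplete cases. Unweighted GEE generally needs data missing completely at random. The mixed model is exploratory only. Imputation is optional, and the data that would best inform it are in the unreturned diary.

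**Illustration of size.** The documents give no stopping rate and no figure for this bias, so there is nothing to reproduce.

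Inputs from Sample size and statistical power: mean nausea severity 6.20 (taken here as the control mean) and a difference of 1, so the intervention mean is 5.20. Assumed: a share p of each arm stops, and stoppers have mean severity 8.

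Observed mean among those remaining = (arm mean − p × 8) / (1 − p).

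- Control, p = 20%: (6.20 − 1.60) / 0.80 = 5.75
- Control, p = 10%: (6.20 − 0.80) / 0.90 = 6.00
- Intervention, p = 10%: (5.20 − 0.80) / 0.90 = 4.89
- Intervention, p = 20%: (5.20 − 1.60) / 0.80 = 4.50

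| Stopping, control / intervention | Observed difference (true 1.00) |
|---|---|
| 20% / 10% | 5.75 − 4.89 = 0.86 |
| 10% / 10% | 6.00 − 4.89 = 1.11 |
| 20% / 20% | 5.75 − 4.50 = 1.25 |
| 10% / 20% | 6.00 − 4.50 = 1.50 |

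The first row loses 14% of the effect. Equal stopping inflates the difference because a severity of 8 lies further above the intervention mean. If stoppers instead lie equally far above their own arm mean (1.8 points: 8.0 and 7.0) and 20% stop in each arm, the intervention mean is (5.20 − 1.40) / 0.80 = 4.75. The difference is then 5.75 − 4.75 = 1.00, with no bias.

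**Second illustration, by simulation.** Here stopping depends only on the score. Plan inputs: mean 6.20, SD 2.44, difference 1. Assumed: normal scores, within-patient correlation 0.3 to 0.7, and a score of 8 or more leading to a stop before the next visit with the probability shown.

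| Stop probability after a severe cycle | Missing at T4, control / intervention | Observed T4 difference |
|---|---|---|
| 10% | 6-7% / about 4% | 0.94-0.95 |
| 30% | 17-19% / 10-11% | 0.82-0.88 |
| 50% | 26-29% / 15-17% | 0.71-0.78 |

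Under this mechanism the effect shrinks. The number of self-management behaviors could not be illustrated, because the plan gives no mean or SD for it.

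**The case against.** Much can be said for the plan. Weekly contact does not depend on a visit, and staff training covers data collection by phone. Admissions are captured by phone with reason and length of stay, so dehydration or a fall leading to admission would be seen. Data given before stopping are kept: someone who stops after Cycle 2 has already supplied T2 and the first diary, and the longitudinal analysis can use them. A hospital stay on the visit date may only delay collection. No text withdraws participants who stop; their loss is inferred from silence.

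All of this stands, and it rules out several stronger readings:
- A reader might infer that every questionnaire depends on a visit. Admissions and game appeal do not.
- A reader might infer that anyone who stops lacks all of T2 to T4. That is true only of those who stop after Cycle 1.
- A reader might infer that recording a delay requires attendance. The research nurse also works from the medical record, and nothing says the patient must be present.

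There is also a fair objection to simply continuing collection. The SRQ asks about the past week. Once chemotherapy has stopped, later scores describe nausea off treatment, which is a different quantity. The first missed time point is different: at the planned date of the next cycle, past-week recall covers the same part of the cycle just received as it does in attenders.

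What remains is that neither primary endpoint, nor QOL, has a stated route at that first missed point, and the completed diary has no way back.

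**Conclusion.** The point holds in this limited form. For permanent stopping or a skipped cycle, the plan states no way to retrieve the completed SMC or to obtain the SRQ and EORTC for the cycle just received. Because the protocol names departure from treatment as an effect of nausea and vomiting, the loss can be informative, and neither oversampling nor optional imputation recovers it.

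Size and direction are unknown. With the plan's mean and a true difference of 1, the assumed scenarios give observed differences from 0.71 to 1.50. The result depends on stopping rates and stopper severity that the documents do not give. The 20% allowance covers attrition in general and is not a CINV-related stopping rate.

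A reader might infer that the effect must be understated, perhaps by about a third. The documents do not support that. With 20% / 10% stopping, such a loss needs arm means of 5.0 and 4.0, giving 4.25 − 3.56 = 0.69; the plan's own mean gives 0.86, and equal stopping can push the difference the other way. Confidence is high about the missing route and low about the amount of bias.

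**What to change.** 1. Set a planned calendar date for T2, T3 and T4 for each participant from the cycle length scheduled at enrolment, with a stated window.
2. If the cycle is not given within that window, retrieve the completed SMC by prepaid envelope. Collect the SRQ and EORTC for that time point by mail or at the existing weekly call.
3. Record the stop date and reason (CINV or other) by arm, using the medical record where needed.
4. Continue assessments to the planned T4 date and flag those made off chemotherapy.
5. State whether the primary comparison covers all randomised participants regardless of chemotherapy or only on-chemotherapy cycles, and give the other as a sensitivity analysis.

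The cost is protocol wording, envelopes, and some questionnaires by phone or mail. Clinical care is unchanged. There are two downsides. Mode of administration differs for a few assessments, and off-treatment scores do not measure CINV during chemotherapy, which is why steps 4 and 5 keep them identifiable. Diary return and the first missed SRQ/EORTC are the parts that most clearly recover lost data.
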